10.5. Appendix 5: Protocol Specific Appendices

Sidekick Health IBD App

At the end of the study (ie, after completing Week 16), study participants will be asked to complete the user version of the Mobile Application Rating Scale (uMARS)⁵⁴ to rate the Sidekick Health IBD App used in this study. A shortened version of the uMARS including only sections A-E will be used. Thus, the questionnaire will include 23 questions separated into 5 sections including App engagement, functionality, aesthetics, information and participants' subjective App quality assessment. Completion of this questionnaire will not be mandatory as per study protocol, ie, study participants can choose to not respond to this questionnaire. Missing data will therefore not be considered protocol deviation.

All study related data collected on the App will be stored on the App provider's cloud-based platform in Belgium during the entire study duration and will be imported to the study database in Switzerland on a regular basis. Study related will be transferred to the Sponsor in a coded form and data are entirely owned by the Sponsor of the study. At the end of the study, the data will be deleted from the Sidekick Health database and this data destruction will be documented in a relevant certificate of destruction. Data collected on the App and transferred to the study database, will be archived together with other study data according to applicable regulations.

Participants who choose to use the functionalities from the native (non-research) version of the Sidekick Health IBD App (eg, IBD-specific modules, activity logging, food diary), which are freely accessible to study participants via their App research account, and thereby choose to provide personal information, such as information about their diet, physical activity, vital signs, etc., will be informed that all these non-research data will be collected and stored by Sidekick Health. Importantly, these non-research data collected via native App functionalities will not be linked to the research data or to individual study participants. Sidekick Health might, at the end of the study, use the data collected via native App functionalities to assess the usability of these App features by the study participants during the study duration. All data collected and assessed will be anonymized and expressed in an aggregated form.

The Full Terms and Conditions and Privacy Policy of Sidekick Health are available under the following links: <https://legal.sidekickhealth.com/2/en/terms.html> and <https://legal.sidekickhealth.com/2/en/privacy.html>, respectively.

10.6. Appendix 6: Abbreviations

The following is a list of abbreviations used in the protocol:

Table 8. Abbreviations

Abbreviation	Definition
AE	adverse event
ALT	alanine aminotransferase
App	mobile application
AST	aspartate aminotransferase
BASEC	Business Administration System for Ethical Committees
BMI	body mass index
CD	Crohn's Disease
CIOMS	Council for International Organizations of Medical Sciences
CK	creatine kinase
CRF	case report form
CRO	contract research organization
CRP	C-reactive Protein
CSR	Clinical Study Report
CT	clinical trial
DILI	drug-induced liver injury
eCRF	electronic case report form
EDB	exposure during breastfeeding

Abbreviation	Definition
EDC	electronic data capture
EDP	exposure during pregnancy
EIM	extra-intestinal manifestation
EMA	European Medicines Agency
EU	European Union
EudraCT	European Union Drug Regulating Authorities Clinical Trials Database
FACIT-F	Functional Assessment of Chronic Illness Therapy - Fatigue
fCAL	fecal calprotectin
FMS	Full Mayo score
FOPH	Federal Office of Public Health
GCP	Good Clinical Practice
GGT	gamma glutamyl transferase
HCP	healthcare provider
HIPAA	Health Insurance Portability and Accountability Act
HRA	Human Research Act
HRO	Human Research Ordinance
HRQL	health-related quality of life
IBD	inflammatory bowel disease
IBDQ	inflammatory bowel disease questionnaire
IBS	irritable bowel syndrome
ICD	informed consent document

Abbreviation	Definition
ICH	International Council for Harmonisation
ID	identification
INR	international normalized ratio
IRB	Institutional Review Board
ITT	intent-to-treat
IUS	intestinal ultrasound
JAKi	Janus Kinase inhibitor
LFT	liver function test
LIS2	low-Interventional Study 2
MCID	minimal clinically important difference
MSR	Medical & Scientific Relations manager
NA	not applicable
NRS	numerical rating scale
pCRF	paper case report form
PMS	Partial Mayo score
POC	point of care
PP	per-protocol
PRO	patient reported outcome
PT	prothrombin time
QoL	quality of life
RRI	research related injury
RW	real world

Abbreviation	Definition
RWD	real world data
RWE	real world evidence
SAE	serious adverse event
SAP	Statistical Analysis Plan
SDV	source data verification
SIV	site initiation visit
SNCTP	Swiss National Clinical Trials Portal
SoA	schedule of activities
SOC	standard of care
SOP	standard operating procedure
SRSD	single reference safety document
SUSAR	Suspected Unexpected Serious Adverse Reaction
TBili	total bilirubin
TLS	Transport Layer Security
TNF	tumor necrosis factor
TNFi	tumor necrosis factor inhibitor
UC	ulcerative colitis
ULN	upper limit of normal
VAS	visual analogue scale
W# (where # is a number)	Week # of study
WOCBP	woman of childbearing potential

2.1 Background and rationale

A number of studies have been published demonstrating tofacitinib's safety and efficacy profile in ulcerative colitis (UC) [1-8]. While it is known that tofacitinib therapy is associated with a rapid onset of symptom relief in terms of the Partial Mayo score (PMS) components (stool frequency and rectal bleeding), the response of other important patient-reported outcomes (PROs), such as fatigue, urgency and abdominal pain, are less well characterized [9, 10]. Measuring these PROs will provide a broader understanding of how patients experience response to tofacitinib treatment. Moreover, the response of intestinal inflammation to tofacitinib induction therapy is currently not fully understood [11]. Regular measurements of fecal calprotectin (fCAL) levels, a widely used biomarker in UC, will provide a measure of the response of intestinal inflammation to tofacitinib treatment. Early measurements will assess the validity of fCAL as an early biochemical predictor of treatment response.

2.2 Objectives

This study aims to generate granular real-world data on tofacitinib therapy in UC and enable a characterization of the relationship between changes in PMS, PROs and intestinal inflammation during tofacitinib induction therapy.

CTU Bern	SAP for: Study A3921395 KIC-START	Version: 1.0
CTU Bern	Template: Statistical Analysis Plan (SAP) Code: CS_STA_TEM-11	Version: 03 Valid from: 28.02.2019 Page 7 of 44

3. Study methods

3.1 Trial design

This study is a single-arm, open-label, prospective, low-interventional, multi-center study conducted in Switzerland in a real-world setting without any comparison groups. Approximately 60 participants were planned to be enrolled. However, following the termination decision as per Pfizer CT26-GSOP, recruitment was prematurely stopped after the enrollment of 18 patients. Please see Section 9 for details on the resulting changes to endpoints and analysis specified in the protocol.

3.2 Randomization

Not applicable.

3.3 Sample size

The initial sample size calculation was shown in the final version of the protocol (22 March 2022). According to that calculation, a total of approximately 60 participants were planned to be enrolled into the study. However, following an internal decision by Pfizer, recruitment was prematurely stopped after the enrollment of 18 patients.

We expect that 60% of participants will achieve a clinical response at Week 8. As noted in the protocol, a sample of 60 participants would have result in a 2-sided 95% Wilson confidence interval around a frequency of 60% from 47.4 to 71.4%. A sample of 18 participants will result in a 2-sided 95% Wilson confidence interval around a frequency of 60% from 37.6 to 78.9%.

3.4 Framework

This is a descriptive single-arm study, there will be no formal hypothesis testing.

3.5 Statistical interim analyses and stopping guidance

Not applicable.

3.6 Timing of final analysis

Final analysis will be performed after database lock.

3.7 Timing of outcome assessments

All outcomes will be analyzed collectively after study completion. After completion of data entry, data validation and cleaning will be performed. Data analysis will start after database lock.

3.8 Blinding

The study is unblinded.

CTU Bern	SAP for: Study A3921395 KIC-START	Version: 1.0
CTU Bern	Template: Statistical Analysis Plan (SAP) Code: CS_STA_TEM-11	Version: 03 Valid from: 28.02.2019 Page 8 of 44

4. Data management

4.1 Data export

The Data Management system used in this study is a dedicated electronic data capturing (EDC) system, secuTrial. The EDC system is activated for the study only once a formal test procedure has been passed successfully. All data entered in the EDC system are stored on a Linux server in a dedicated Oracle database at Inselspital Bern, Switzerland.

Clinical study data will be provided by CTU Bern (Clinical Trial Unit of the University of Bern) in a database format (secuTrial®) and will be imported into R by the study statistician for data preparation, validation, and analysis.

4.2 Data validation

First line data validation is performed by the online Case Report Form (eCRF) system in real-time as defined in the data dictionary. Second line data validation and cleaning will be performed according to the Standard Operating Procedure (SOP) for data validation [13] after the completion of overall data collection, before database export for the final analysis.

4.3 Data preparation

Table 4-a: Data preparation

Variable definition	Variable type	Derivation
Baseline date: date of first medication intake	Date (dd.mm.yyyy)	pro_medi_start_date
Prior exposure to TNFi, vedolizumab and ustekinumab;	Binary (yes, no)	Used variables: th_ustekinumab th_vedolizumab th_tnfi Visit: Baseline. Derivation - General: 'yes' if at least one of the above variables is different from 'Never prescribed'; 'No' otherwise. - if missing data (i.e., at least one of the 3 variables mentioned above is missing): 'yes' if at least one of the above variables is different from "Never prescribed"; 'NA' otherwise.
Concomitant medication with corticosteroids or aminosalicylic acids	Binary (yes, no)	Used variables: cm_drug.factor cm_start cm_end pro_medi_start_date Derivation If cm_drug.factor contains "Topical corticosteroids" OR "Oral corticosteroids" OR "Topical aminosalicylates" OR "Oral aminosalicylates"

CTU Bern	SAP for: Study A3921395 KIC-START	Version: 1.0
----------	-----------------------------------	--------------

CTU Bern	Template: Statistical Analysis Plan (SAP)	Version: 03	Page 9 of 44
	Code: CS_STA_TEM-11	Valid from: 28.02.2019	

Variable definition	Variable type	Derivation
		AND if one of the mentioned above drugs is taken at the pro_medi_start_date (i.e. pro_medi_start_date %in% [cm_start, cm_end])
Concomitant use of Ustekinumab	Binary (yes, no)	Used variables: cm_drug.factor cm_start cm_end pro_medi_start_date Derivation If cm_drug.factor contains "Ustekinumab" AND if one of the mentioned above drugs is taken at the pro_medi_start_date (i.e. pro_medi_start_date %in% [cm_start, cm_end])
Concomitant use of Vedolizumab	Binary (yes, no)	Used variables: cm_drug.factor cm_start cm_end pro_medi_start_date Derivation If cm_drug.factor contains "Vedolizumab" AND if one of the mentioned above drugs is taken at the pro_medi_start_date (i.e. pro_medi_start_date %in% [cm_start, cm_end])
Concomitant use of TNF inhibitors	Binary (yes, no)	Used variables: cm_drug.factor cm_start cm_end pro_medi_start_date Derivation If cm_drug.factor contains "TNF inhibitors" AND if one of the mentioned above drugs is taken at the pro_medi_start_date (i.e. pro_medi_start_date %in% [cm_start, cm_end])
Concomitant use of Tacrolimus	Binary (yes, no)	Used variables: cm_drug.factor cm_start cm_end pro_medi_start_date Derivation If cm_drug.factor contains "Tacrolimus" AND if one of the mentioned above drugs is taken at the pro_medi_start_date (i.e. pro_medi_start_date %in% [cm_start, cm_end])
Concomitant use of Cyclosporin	Binary (yes, no)	Used variables: cm_drug.factor cm_start cm_end pro_medi_start_date Derivation If cm_drug.factor contains "Cyclosporin" AND if one of the mentioned above drugs is taken at the pro_medi_start_date (i.e. pro_medi_start_date %in% [cm_start, cm_end])
Concomitant use of Methotrexate	Binary (yes, no)	Used variables: cm_drug.factor cm_start cm_end pro_medi_start_date

CTU Bern	SAP for: Study A3921395 KIC-START	Version: 1.0
----------	-----------------------------------	--------------

CTU Bern	Template: Statistical Analysis Plan (SAP)	Version: 03	Page 10 of 44
	Code: CS_STA_TEM-11	Valid from: 28.02.2019	

Variable definition	Variable type	Derivation
		Derivation If cm_drug.factor contains "Methotrexate" AND if one of the mentioned above drugs is taken at the pro_medi_start_date (i.e. pro_medi_start_date %in% [cm_start, cm_end])
Concomitant use of Thiopurines	Binary (yes, no)	Used variables: cm_drug.factor cm_start cm_end pro_medi_start_date Derivation If cm_drug.factor contains "Thiopurines" AND if one of the mentioned above drugs is taken at the pro_medi_start_date (i.e. pro_medi_start_date %in% [cm_start, cm_end])
Concomitant use of aminosalicylates	Binary (yes, no)	Used variables: cm_drug.factor cm_start cm_end pro_medi_start_date Derivation If cm_drug.factor contains "Oral / topical aminosalicylates" AND if one of the mentioned above drugs is taken at the pro_medi_start_date (i.e. pro_medi_start_date %in% [cm_start, cm_end])
Concomitant use of steroids	Binary (yes, no)	Used variables: cm_drug.factor cm_start cm_end pro_medi_start_date Derivation If cm_drug.factor contains "Topical corticosteroids" OR "Oral corticosteroids" AND if one of the mentioned above drugs is taken at the pro_medi_start_date (i.e. pro_medi_start_date %in% [cm_start, cm_end])
Concomitant use of low dose steroids	Binary (yes, no)	Used variables: cm_drug.factor cm_start cm_end pro_medi_start_date cm_dose Derivation If cm_drug.factor contains "Topical corticosteroids" OR "Oral corticosteroids" AND if one of the mentioned above drugs is taken at the pro_medi_start_date (i.e. pro_medi_start_date %in% [cm_start, cm_end]) with the dose (i.e. cm_dose) %in% c('Systemic: < 15mg/day prednisone equivalent', 'Locally- acting: < 3mg/day budesonide')
Concomitant use of high dose steroids	Binary (yes, no)	Used variables: cm_drug.factor cm_start cm_end pro_medi_start_date cm_dose Derivation If cm_drug.factor contains "Topical corticosteroids" OR

CTU Bern	SAP for: Study A3921395 KIC-START	Version: 1.0
----------	-----------------------------------	--------------

CTU Bern	Template: Statistical Analysis Plan (SAP)	Version: 03
	Code: CS_STA_TEM-11	Valid from: 28.02.2019

Variable definition	Variable type	Derivation
		
“Oral corticosteroids” AND if one of the mentioned above drugs is taken at the <code>pro_medi_start_date</code> (i.e. <code>pro_medi_start_date</code> %in% <code>[cm_start, cm_end]</code>) with the dose (i.e. <code>cm_dose</code>) %in% c('Systemic: ≥ 15mg/day prednisone equivalent', 'Locally-acting: ≥ 3mg/day budesonide')

Baseline predominant tofacitinib dose	Binary (<15mg tofacitinib/day, ≥15 mg tofacitinib/day)	
Variable: <code>te_bl_dose.factor</code> <code>te_bl_dose_oth_value</code> <code>te_bl_dose_oth_unit</code>
 
Visit: Baseline.
 
Derivation <code>'yes'</code> if <code>te_bl_dose.factor == '10 mg twice daily'</code> OR <code>te_bl_dose.factor == 'Other'</code> & <code>(te_bl_dose_oth_value & te_bl_dose_oth_unit <15 mg/day)</code>; otherwise 'no'.

Average daily dose of Tofacitinib during the trial	Binary (<15mg tofacitinib/day, ≥15 mg tofacitinib/day)	
Variable: <code>te_bl_dose.factor</code> <code>te_bl_dose_oth_value</code> <code>te_bl_dose_oth_unit</code> <code>te_dose</code> <code>te_other_value</code> <code>te_other_unit</code> <code>te_start</code> <code>te_end</code> <code>te_disc_date</code>
 
Derivation: Calculation of the mean daily dose of tofacitinib and categorization as < 15mg/day or ≥ 15mg/day

IBDQ score	Continuous (score varying between from 32 to 224)	
Variables: <code>pro_ibdq_x</code> (with X varying from 1 to 32)
 
Derivation: at each reported time point. For each variable, 7 answers are possible. Answers are ranked from the 'worst' to 'best' quality of life, and replaced by a score varying from 1(worst) to 7(best). Scores obtained for each of the 32 variables are then summed up. If any of the <code>pro_ibdq_x</code> (with X varying from 1 to 32) variables is missing the score is coded as missing.

Weekly fatigue score (FACT-F score)	Continuous (score varying between from 0 to 52)	
Variables <code>pro_facit_an1, pro_facit_an2, pro_facit_an3, pro_facit_an4, pro_facit_an5, pro_facit_an7, pro_facit_an8, pro_facit_an12, pro_facit_an14, pro_facit_an15, pro_facit_an16, pro_facit_hi12, pro_facit_hi7</code>
 
Derivation: at each reported time point. For each variable, 5 answers are possible. Answers are converted to score (see below), scores obtained for each of the 13 listed variables are then summed up. If any of the variables use to derive the score is missing the score is coded as missing.

CTU Bern	SAP for: Study A3921395 KIC-START	Version: 1.0

CTU Bern	Template: Statistical Analysis Plan (SAP)	Version: 03	Page 12 of 44
	Code: CS_STA_TEM-11	Valid from: 28.02.2019	

Variable definition	Variable type	Derivation
		Scoring system: Not at all =0; A little bit =1; Somewhat =2; Quite a bit =3; Very much =4
PMS score	Continuous	Variables: pms_stool_freq, pms_rect_bleed, pms_glob_ass Derivation: At each reported time point. For each variable, 4 answers are possible. Answers are converted to score from 0 (normal) to 3 (more severe condition), scores obtained for each of the 3 listed variables are then summed up. If any of the variables used to derive the score is missing the score is coded as missing.
PMS stool frequency subscore	Continuous	Variable: pms_stool_freq Derivation: At each reported time point. 4 answers are possible. Answers are converted to score from 0 (normal) to 3 (more severe condition).
PMS rectal bleeding subscore	Continuous	Variable: pms_rect_bleed Derivation: At each reported time point. 4 answers are possible. Answers are converted to score from 0 (normal) to 3 (more severe condition).
PMS physician's global assessment subscore	Continuous	Variable: pms_glob_ass Derivation: At each reported time point. 4 answers are possible. Answers are converted to score from 0 (normal) to 3 (more severe condition).
Full Mayo score	Continuous	Variables: PMS score (see above), ra_mayo_subscore Derivation: At each reported time point. For each variable, 4 answers are possible for the ra_mayo_subscore variable. Answers are converted to score from 0 (normal) to 3 (severe disease), scores obtained for the PMS score and the ra_mayo_subscore variable are then summed up. If any of the variables used to derive the score is missing the score is coded as missing.
Participant's age	Continuous	Used variables: ic_date, ymob Derivation: Date of signature of the informed consent in mm.yyyy – the date of birth in mm.yy. Result is given in year and rounded to one decimal point
EIM improvement status at week_x (x can be equal to 8 or 16)	Continuous	Variables: eim_cat, eim_subcat_muco, eim_subcat_muscu, eim_subcat_ocular, eim_subcat_hepa, eim_activity Derivation: For each EIM (defined by the variables eim_cat, eim_subcat_muco, eim_subcat_muscu, eim_subcat_ocular, eim_subcat_hepa) -'No worsening' if

CTU Bern	SAP for: Study A3921395 KIC-START	Version: 1.0
----------	-----------------------------------	--------------

CTU Bern	Template: Statistical Analysis Plan (SAP)	Version: 03
	Code: CS_STA_TEM-11	Valid from: 28.02.2019

Variable definition	Variable type	Derivation
		<pre>eim_activity at baseline ='Active at assessment' AND eim_activity at week_x ='Active at assessment' OR eim_activity at baseline ='Past, but not active' AND eim_activity at week_x ='Past, but not active' OR EIM at baseline AND EIM not mentionned at week_x -'Worsened' if eim_activity at baseline ='Past, but not active' AND eim_activity at week_x ='Active at assessment' -'Improved' if eim_activity at baseline ='Active at assessment' AND eim_activity at week_x ='Past, but not active' -'New occurrence' if No EIM at baseline AND eim_activity at week_x ='Active at assessment'</pre>
Number of comorbidities	Continuous	
Used variables:
 
co_morb_yn co_morb
 
Derivation: at bl, W8 and 16.
 
If co_morb_yn== 'yes' count the number of different entries for co_morb If co_morb_yn== 'no' 0

Number of EIMs	Continuous	
Used variables:
 
eim_yn
 
Derivation: at bl, W8 and 16.
 
If eim_yn== 'yes' count the number of different entries for EIM If eim_yn== 'no' 0

uMARS score	Continuous	
Sum all uMARS answers (variables names not available at the time of writing the SAP).
 
If any of the variables use to derive the score is missing, the score is coded as missing.

090177e1a1762bcf\Final\Final On: 22-Aug-2024 18:32 (GMT)

CTU Bern	SAP for: Study A3921395 KIC-START	Version: 1.0
----------	-----------------------------------	--------------

CTU Bern	Template: Statistical Analysis Plan (SAP)	Version: 03	Page 14 of 44
	Code: CS_STA_TEM-11	Valid from: 28.02.2019	

5. Statistical principles

5.1 Confidence intervals and *P* values

All confidence intervals will be two-sided and relate to the 95% level and the two-sided significance level will be set at $\alpha = 0.05$.

5.2 Analysis populations

5.2.1 Full analysis set (FAS)

The full analysis set (FAS), will include all participants who were included in the study (i.e., performed baseline visit and received a study identification number). This analysis will therefore include all study participants, regardless of their adherence to study protocol procedures.

5.2.2 Per-protocol analysis set (PP)

Not applicable.

5.2.3 On-tofacitinib analysis set (OTAS)

The on-tofacitinib analysis set consists of all participants in the FAS set who did not stop or interrupt the tofacitinib therapy before the 8 weeks visit.

Table 5-a: Derivation of protocol deviations

Protocol deviation	eCRF sheet	Variable	Variable type	Derivation
Completion of the therapy until the W8 visit	Binary (yes, no)	Used variables: Time to tofacitinib discontinuation (see above) Date of the 8 weeks visit Derivation 'yes' if Time to tofacitinib discontinuation (see above) < Date of the 8 weeks visit	Completion of the therapy until the W8 visit	Binary (yes, no)

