6.6 Adherence and protocol deviations

Adherence to study protocol and to tofacitinib will not be assessed.

Main analysis will be conducted on the full analysis set (FAS). Secondary analysis will include all study participants who did not stop or interrupt the tofacitinib therapy before the week 8 visit (i.e OTAS set, see section 5.2.3).

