response according to IUS assessment at W8/W16.	According to treating physician's assessment of bowel wall thickness, normalization and extension; bowel wall vascularity, loss of stratification, loss of colonic hastration, structure formation and hyperechoic reaction adjacent to the bowel wall.	SOC Assessment	ra_global_eval	categorical	Yes: ra_global_eval %in% c('response', 'remission')	Binary: Yes, no
remission according to IUS assessment at W8/W16.	According to treating physician's assessment of bowel wall thickness, nor-	SOC Assessment	ra_global_eval	categorical	Yes: ra_global_eval = 'remission'	Binary: Yes, no

CTU Bern	SAP for: Study A3921395 KIC-START	Version: 1.0
----------	-----------------------------------	--------------

CTU Bern	Template: Statistical Analysis Plan (SAP)	Version: 03
Code: CS_STA_TEM-11	Valid from: 28.02.2019	Page 28 of 44

u^b^b
UNIVERSITÄT
BERN

Outcome	Definition	eCRF sheet	Variable	Variable type	Derivation	Outcome type
	malization and extension; bowel wall vascularity, loss of stratification, loss of colonic haustration, structure formation and hyperecho- genic reaction adjacent to the bowel wall.					
individual improvement in EIM reported at BL at W8/W16 15 outcome/variables	EIM improvement for EIM reported at BL	Extra Intestinal Manifestations (EIM)	eim_cat eim_subcat eim_activity ('Past, but not active' vs. active at assessment)	-Categorical -Categorical - Binary	See section 4.3 for EIM improvement status at week_x (x can be equal to 8 or 16) Yes: EIM improvement status == Improved	Binary: Yes, no
Categorical improvement 5 variables/outcomes	EIM improvement is reported for at least one of the subcategories of the studied category.	Extra Intestinal Manifestations (EIM)	eim_cat eim_activity ('Past, but not active' vs. active at assessment)	-Categorical - Binary	Yes: eim_cat==the studied category AND eim_activity=='Past, but not active'	Binary: Yes, no
ADDITIONAL EXPLORATORY OUTCOMES						
Average daily dose of Tofacitinib during the trial		Baseline Tofacitinib Change in Tofacitinib Exposure			See section 4.3	Binary: <15mg tofa-citinib/day,

CTU Bern	SAP for: Study A3921395 KIC-START	Version: 1.0
----------	-----------------------------------	--------------

CTU Bern	Template: Statistical Analysis Plan (SAP)	Version: 03
	Code: CS_STA_TEM-11	Valid from: 28.02.2019

u^b^b
UNIVERSITÄT
BERN

Outcome	Definition	eCRF sheet	Variable	Variable type	Derivation	Outcome type
	Tofacitinib discontinuation					≥15 mg tofacitinib/day

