7.2.2 Secondary analyses

If more than 2 patients are excluded from the on-tofacitinib analysis set (OTAS), all analysis described in the primary analysis section above will be conducted on the OTAS population.

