8.5 Safety Data

8.5.1 Summary of AEs

	All Causalities	Treatment Related
Number of AEs		
Subjects with AEs [n (%)]		
Subjects with SAEs ^a [n (%)]		
Subjects with severe AEs ^b [n (%)]		
Subjects permanently withdrawn from tofocitinib due to AEs ^c [n (%)]		
Subjects with tofacitinib dose reduced or temporary discontinuation tofacitinib due to AEs [n (%)]		

Footnotes:

Included events from study database, even those that occurred after discontinuation of drug under study. Except for the number of AEs, subjects were counted only once per treatment in each row.

a. SAEs were determined according to the investigator's assessment.

b. Severity counts were based on the maximum severity or grade of events.

c. Discontinuation of tofacitinib due to AE based on the AE CRF is summarized, and numbers shown include subjects withdrawn for an AE of UC.

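### SAP Table 5-a marks early stoppers of tofacitinib as having completed therapy to Week 8, contrary to its row label and to the OTAS definition

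*SAP*

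**What the plan says.** Section 5.2.3 of the SAP restricts OTAS to FAS participants who "did not stop or interrupt the tofacitinib therapy before the 8 weeks visit". Section 6.6 repeats this: "Secondary analysis will include all study participants who did not stop or interrupt the tofacitinib therapy before the week 8 visit". Protocol section 9.5.2 points the same way, asking for the analyses to be repeated in those who complete 8 weeks of tofacitinib.

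The only operational rule is Table 5-a, printed under 5.2.3 and titled "Derivation of protocol deviations". Its single row is labelled as completion of therapy up to the Week 8 visit. The flag is 'yes' if "Time to tofacitinib discontinuation (see above) < Date of the 8 weeks visit".

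Section 7.2.2 makes the OTAS analyses conditional. They are run "If more than 2 patients are excluded from the on-tofacitinib analysis set (OTAS"). Section 3.3 gives the number enrolled: "recruitment was prematurely stopped after the enrollment of 18 patients".

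**The concern.** A completion flag should be 'yes' for someone still on drug at the Week 8 visit. The printed inequality gives 'yes' to someone who stopped before it. The SAP never states which value of the flag puts a participant into OTAS, so nothing in the text resolves the conflict.

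The same cell has four other faults:

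- It refers back to a time to discontinuation that is not derived anywhere in the SAP. The discontinuation date, `te_disc_date`, appears only as an input to the average daily dose in Table 4-a.
- It compares a time with a calendar date.
- It ignores interruptions, which the definition excludes. The SAP does expect such data: Table 7-a lists an eCRF sheet "Change in Tofacitinib Exposure", and section 8.5.1 has a row "Subjects with tofacitinib dose reduced or temporary discontinuation tofacitinib due to AEs".
- It says nothing about participants who never stop or who have no Week 8 visit.

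Both the membership of OTAS and the trigger in 7.2.2 depend on this status. Under protocol section 7.1, participants who stop the drug remain in the study, so early stoppers are in the FAS and can have Week 8 data. OTAS is also the only alternative population left: the SAP drops the per-protocol set and plans no sensitivity or subgroup analyses. The quality control in section 7.8 reproduces the primary analysis, so it would not necessarily catch an inverted secondary set.

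**Working it through.** There is no planned figure to reproduce here, because the point concerns the direction and coverage of a rule.

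**Step 1: classify example participants.** Assume that the Week 8 visit falls on its nominal day 56 (protocol Table 1).

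| Participant | Table 5-a as printed | OTAS by the prose |
|---|---|---|
| Stops day 20 | yes | out |
| Stops day 55 | yes | out |
| Stops day 56 | no | in |
| Stops day 80 | no | in |
| Never stops | undefined | in |
| Interrupts days 20–30, resumes | undefined | out |

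All four participants with a stopping day are classified opposite to the row label. They are also opposite to the OTAS prose if 'yes' means included.

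**Step 2: count the set and the trigger, with 'yes' meaning included.** Let N = 18 and let k be the number who stop before the Week 8 visit. The documents do not give k, so the range 0 to 18 is used. Assume no interruptions, and assume that a participant with no discontinuation date does not meet the inequality.

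- Prose: excluded = k; OTAS = 18 − k; analysis runs if k > 2.
- Table taken literally: excluded = 18 − k; OTAS = k; analysis runs if 18 − k > 2, so k ≤ 15.

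| k | Prose | Table taken literally |
|---|---|---|
| 0, 1, 2 | does not run | runs, on 0, 1 or 2 people |
| 3 | runs, on 15 | runs, on 3 |
| 4 | runs, on 14 | runs, on 4 |
| 3 to 15 in general | runs, on 18 − k | runs, on the other k |
| 16, 17, 18 | runs, on 2, 1 or 0 | does not run |

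The run decision differs for 6 values of k (0, 1, 2, 16, 17, 18). For the other 13 values both run, but on complementary sets. 6 + 13 = 19, so no value of k gives the defined analysis.

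**Step 3: take 'yes' as a deviation instead.** 'Yes' participants are then excluded and OTAS = 18 − k, which is correct for stopping. Now let m participants interrupt and resume without stopping (m is also assumed).

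- Prose: excluded = k + m.
- Rule: excluded = k.
- The trigger is missed when k ≤ 2 and k + m ≥ 3. The smallest cases (k, m) are (2, 1), (1, 2) and (0, 3).

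For k = 2 and m = 1, the prose excludes 3 and the analysis runs. The rule excludes 2 and it does not. Where the analysis does run, the m interrupters stay in a set that should exclude them.

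**Step 4: participants with no Week 8 visit.** They have no Week 8 partial Mayo score, and section 7.4 ignores missing data, so their classification does not move the Week 8 response proportion. It can change the trigger count and the earlier calprotectin and patient-reported summaries. If they attend Week 16, it can also change the Week 16 OTAS results.

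**The case against.** The strongest reply is that only the conflict between label and rule is proven. The table's title refers to deviations, and if 'yes' means that a deviation occurred, the inequality points the right way and only the label is wrong. The prose definition is clear and stated twice, 7.2.2 refers to OTAS and not to the table, and a programmer who follows the prose builds the right set. The enumeration over k restates a reversed sign and does not measure likely harm. It also rests on treating participants without a discontinuation date as 'no', which the rule does not say. An on-tofacitinib set made up of a handful of early stoppers would probably be noticed. The study is descriptive, and OTAS is secondary and conditional.

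Much of this stands as a limit on the consequence. The conflict with the OTAS definition does require reading 'yes' as inclusion, which is the natural use of a completion flag printed under the set it serves but is not stated. The reply does not rescue the rule, however. Under the deviation reading the label is still wrong and interruptions are still not captured, so the rule does not implement the definition either way. One further caution is fair: `te_start` and `te_end` are listed only as dose inputs, and the row in 8.5.1 covers only adverse-event-related cases and groups them with dose reductions. That these variables record every interruption has to be confirmed.

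**Conclusion.** The concern holds and should be fixed. Table 5-a is wrong as written, not merely short of detail. Its rule opposes its own label on any reading, opposes the OTAS definition when 'yes' means included, and omits interruptions in every case. Taken literally, with 18 participants, no interruptions, and non-stoppers counted as not 'yes', it never yields the defined analysis. The actual effect cannot be stated, because the numbers of stoppers and interrupters are not in the documents.

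The primary FAS results are untouched. What is at risk is the OTAS repeat of those analyses and the decision whether to run it.

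**What to change.** Rewrite the row and its links:

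- Set completion to 'yes' if `te_disc_date` is absent, or falls on or after the Week 8 visit date, and the exposure records (`te_start`, `te_end`) show no interruption before that visit. Otherwise set it to 'no'. This compares dates with dates and removes the reference to an underived variable.
- State that OTAS consists of FAS participants with this flag equal to 'yes', and that the trigger in 7.2.2 counts FAS minus OTAS.
- Move the row out from under the deviations title.
- State how participants with no Week 8 visit are classified. That choice is the sponsor's.

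The cost is SAP wording only. The three variables are already listed in Table 4-a, so no new data should be needed, provided a check against the exposure-change eCRF sheet confirms that `te_start` and `te_end` capture interruptions.
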